Patients will be enrolled exclusively based on inclusion and exclusion criteria, undergoing randomization into intervention or control groups. No screening tools will be used.

• STUDY PROCEDURES

The study will be an internally funded, parallel-intervention clinical trial studying the use of lower extremity compression stockings as adjuvant therapy to standard medical care in management of patients admitted for acute systolic heart failure. There will be two arms, intervention and control. 120 patients will be enrolled in the study, 60 to each arm, to achieve power above 80% with an alpha of 0.05, measuring continuous primary endpoints of average percent reduction in weight after diuresis, average change in BNP from admission to discharge, and average length of admission in days.

Data will be collected by Henry Ford personnel, for 120 patients previously admitted after January 2018 and managed on the HF Main cardiology I5 floor meeting inclusion criteria and managed with standard medical therapy without the use of compression stockings, and will undergo review by research team for enrollment into the control group. If additional patients are needed to achieve enrollment number of 60 control subjects, patients will be enrolled and randomized prospectively by the research team. Data collected retrospectively will be performed through Epic health medical record and charted on Excel spreadsheet, and will include admission length of stay, daily weights, daily urine outputs, daily diuretic dose and type(s) used, admission BNP, and discharge BNP. Research team will also perform chart review on enrolled patients to evaluate for 30-day readmission rate.

The intervention arm will include patients enrolled and randomized by the research team meeting inclusion criteria, and managed on HF Main cardiology I5 floor. This population will receive bilateral lower extremity compression wraps (ACE bandages) on day 1 of admission in addition to standard medical therapy. Data will be collected by the research team through Epic health medical record and will be charted on Excel spreadsheet, and will include admission length of stay, daily weights, daily urine outputs, daily diuretic dose and type(s) used, admission BNP, and discharge BNP. These charts will also undergo review by research team to evaluate for 30-day readmission rate.

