Co-investigators will be responsible for retrospective and prospective data review for control population. Both co-investigators and sub-investigators will be responsible for enrolling patients in the study and collecting above mentioned data points. Nursing staff on the floor will undergo teaching on application of ACE compression wraps, and will be responsible for capturing physician order for wrap application and executing order, which will mark the beginning of the trial enrollment.

Data analysis will be conducted through the Division of Biostatistics and Research Epidemiology and will include descriptive statistics and univariate comparisons between treatment groups. T-test and ANOVA with post-hoc analysis will be used to evaluate for difference in the means of each endpoint previously listed for each treatment group. Patient information will be de-

identified prior to data analysis. Data for enrolled patients will be saved on secure Henry Ford Health System servers on Microsoft OneDrive cloud servers and shared among research team. Identifiers will include MRNs to access patient charts, collect and verify data, and perform review for 30-day readmission rates. Data will be stored for the entirety of the study, and promptly discarded in accordance with HFHS regulation at the completion of the study tentatively scheduled for January 2021. Data collected on patients excluded from the study will be discarded at the time of exclusion in accordance with HFHS regulation. Missing or incomplete data will prompt withdrawal of particular patient from study, and will factor into final data analysis as an intention to treat value.

Total time of subject enrollment in the study: duration of hospital stay. No additional visits or follow-up testing is required.

Literacy and language barrier concerns will be handled on a case-by-case basis, primarily using standard communication methods of translator services.

- **ANTICIPATED RISKS**

There are no significant anticipated risk beyond standard of care risk in management of patients with acute systolic heart failure. Intervention includes an already established therapy on patients with lower extremity edema. We are simply testing the formal efficacy of this intervention in an interventional study.

- **ANTICIPATED BENEFITS**

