Anticipated benefits include: decreased length of stay, decreased amount of diuretic used, increased percentage of weight achieved through diuresis; greater percent of BNP reduction; decreased 30-day readmission rate.

- **RENUMERATION/COMPENSATION**

No compensation offered

- **COSTS**

There is no additional cost anticipated for this study outside of standard medical management of acute systolic heart failure and any additional medical conditions treated during the hospital admission.

- **ALTERNATIVES**

Intervention does not involve offering an established efficacious therapy to patients, and conversely control group is not being withheld from any known therapy that affects morbidity/mortality. No known alternatives.

- **CONSENT PROCESS AND DOCUMENTATION**

Co-investigators and sub-investigators enrolling patients will be responsible for obtaining consent from patients prior to enrollment. This will involve presentation of consent document with description of study. Patients will have the opportunity to privately ask questions and receive answers at the time of enrollment after the study is described to them in detail, including risks and benefits. There will be no duress or undue influence, as intervention is already a standard of medical practice. Patients will have the opportunity to refuse intervention. Patients will not be enrolled if they have diminished capacity or learning disability, or impairment of any kind. If patient is non-English speaking, consent form will be translated using standard translator services (in person translator, translator phone). Consent documentation will be stored on the Henry Ford secured OneDrive Microsoft cloud server. This information will only be accessible by research team. Information will be stored for the entirety of the study, and promptly discarded in accordance with HFHS regulation at the completion of the study tentatively scheduled for January 2020. Information collected on patients excluded from the study will be discarded at the time of exclusion in accordance with HFHS regulation.

- **WITHDRAWAL OF SUBJECTS**

Patients withdrawn from study will be notified, and information gathered from enrollment period will be analyzed as intention to treat. All information will be destroyed appropriately at the time of withdrawal.

- **PRIVACY AND CONFIDENTIALITY**

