Patient information will be stored without identifiers. Access to patient chart will be provided to healthcare providers caring for patients during hospitalization, as well as co-investigators and PI of the study. Research team will then use a master key to remove identifiers. Data will be collected and pooled using this master key, and stored on secured HF servers under password protection for use by research team exclusively.

Important HIPAA Concerns

If you will be using, disclosing or accessing the health record (medical record, mental health or substance abuse records, etc) for research purposes, then HIPAA applies. If you are accessing medical records or PHI for screening purposes, HIPAA regulations apply and investigators will need to obtain prospective HIPAA authorization or apply for a waiver of HIPAA authorization for the screening activities, as applicable, depending on the nature of the study.

If accessing PHI for screening purposes and providing written authorization, describe how authorization will be obtained for the screening portion, who will obtain it or request and justification for a request for HIPAA waiver for recruitment purposes. If you are requesting waiver of HIPAA for screening purposes, describe the confidentiality procedures that will be used.

For more information on HIPAA authorization guidance, visit: <https://www.hhs.gov/hipaa/for-professionals/privacy/guidance/research/index.html>

NOTE: You may also need to obtain a waiver of documentation of informed consent (ie, signed consent) for screening purposes if you do not meet the requirements for waiving consent provided in the Consent Process section.

- **DATA AND SAFETY MONITORING PLAN**

PI and co-investigators will be directly involved in the enrollment of each subject. The intervention is low-risk and already a component of standard medical care. Nurses and sub-investigators will be allowed to care for enrolled patients under standard medical care. Each patient will be assessed at the start of enrollment, and at the end of hospitalization for compliance with standard medical care, as is the practice of all patients at Henry Ford Hospital. All adverse events and harm/near miss/sentinel events will be reported immediately to IRB. No such events are anticipated.

- **QUALIFICATIONS OF THE INVESTIGATOR(S)**

Principal Investigator, [name] is an ABMS certified physician in Cardiovascular Medicine, and Internal Medicine.

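### The missing-data and withdrawal rules contradict each other: withdrawn patients are to be analysed by intention to treat, yet all their information is to be destroyed at withdrawal

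*Combined protocol and SAP*

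**What the plan says.** The data paragraph of Study Procedures states that "Missing or incomplete data will prompt withdrawal of particular patient from study", and the same sentence adds that this "will factor into final data analysis as an intention to treat value". It sets no threshold and names no item, and the document nowhere says what such a value is or how it is obtained.

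Withdrawal of Subjects has two relevant sentences, one after the other. The first says that "information gathered from enrollment period will be analyzed as intention to treat". The second says: "All information will be destroyed appropriately at the time of withdrawal".

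The data to which the missing-data rule could apply are listed earlier in Study Procedures. For each arm, collection from the Epic record "will include admission length of stay, daily weights, daily urine outputs, daily diuretic dose and type(s) used, admission BNP, and discharge BNP". For the intervention arm the plan adds: "These charts will also undergo review by research team to evaluate for 30-day readmission rate"; a matching review is planned for controls. The sample size is 60 per arm, "to achieve power above 80% with an alpha of 0.05", with three continuous primary endpoints (percent weight reduction, BNP change, length of stay) and no stated allowance for missing data.

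The control arm is filled first from charts of 120 past admissions reviewed for 60 places. Any shortfall is made up by prospective enrolment and randomisation.

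**The concern.** An intention-to-treat analysis needs the data of withdrawn patients at the final analysis, which comes after withdrawal. A rule that destroys those data at withdrawal removes what the analysis requires.

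The missing-data rule makes this more than a matter for the occasional patient who withdraws consent. It turns incomplete data into a reason for withdrawal, and the data list mixes primary-endpoint items with others such as daily urine output and diuretic dose. If the destruction sentence governs, a patient without a discharge BNP would also lose a known length of stay, any known weight change and, with the study's record of the patient gone, the readmission review. Two of the three primary endpoints would then be analysed on fewer patients than had them recorded.

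There is also a question of balance between the arms. Control places can be refilled from the chart pool or by prospective enrolment, whereas no refill is written for the intervention arm. Replacing incomplete charts with complete ones could select controls on completeness in a way that intervention patients are not selected.

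**Working it through.** **Can the rules be followed together?**

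| Place | Rule | Consequence for a withdrawn patient's recorded values |
|---|---|---|
| Study Procedures | Missing or incomplete data leads to withdrawal | The patient becomes a withdrawn patient |
| Study Procedures, same sentence | Counts as an intention-to-treat value | Stays in the analysis, by an undefined method |
| Withdrawal of Subjects, first sentence | Analysed by intention to treat | Must be kept until the final analysis |
| Withdrawal of Subjects, second sentence | All information destroyed at withdrawal | Not available at the final analysis |

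The last row is incompatible with the two above it. Three possible ways out were checked:

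- *Only identifiers are destroyed.* Privacy and Confidentiality says "Research team will then use a master key to remove identifiers", but that is a separate procedure and does not narrow the destruction sentence.
- *The sentence concerns excluded patients.* They have their own discard rule in Study Procedures and again under the consent heading.
- *Values are taken again from Epic.* The source record survives, but no section provides for re-extraction after withdrawal.

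**What would be lost if destruction governs?**

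The plan's sample size cannot be reproduced, because no effect size or standard deviation is given. The calculation below is therefore an illustration for length of stay.

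Inputs from the plan: 60 per arm, alpha 0.05, power above 80%, comparison of means by t-test.

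Assumptions: two-sided test, equal variances, length of stay known for everyone, and 10, 20 or 30% of an arm withdrawn for some other missing item, leaving 60 × 0.9 = 54, 60 × 0.8 = 48 or 60 × 0.7 = 42.

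Solving for the standardised difference that gives exactly 80% power with 60 per arm yields d = 0.516 (noncentral t). With n₁ intervention and n₂ control patients:

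- Interval width relative to 60/60 = √[(1/n₁ + 1/n₂) / (2/60)] × t(0.975, n₁+n₂−2) / t(0.975, 118), where t(0.975, 118) = 1.980.
- Power comes from the noncentral t with n₁+n₂−2 degrees of freedom and noncentrality d / √(1/n₁ + 1/n₂).

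Two worked cases at 10% loss:

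- Intervention arm only (54/60): √(0.03519/0.03333) × 1.981/1.980 = 1.028.
- Both arms (54/54): √(0.03704/0.03333) × 1.983/1.980 = 1.055.

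| Assumed loss | Intervention/control | Interval wider by | Power |
|---|---|---|---|
| None | 60/60 | 0 | 80.0% |
| 10%, intervention only | 54/60 | 2.8% | 77.8% |
| 20%, intervention only | 48/60 | 6.2% | 75.1% |
| 30%, intervention only | 42/60 | 10.4% | 71.9% |
| 10%, both arms | 54/54 | 5.5% | 75.7% |
| 20%, both arms | 48/48 | 12.1% | 70.6% |
| 30%, both arms | 42/42 | 20.1% | 64.6% |

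The intervention-only rows represent controls refilled to 60 as Study Procedures allows. The both-arms rows represent no refilling. The interval widths do not depend on the true effect; the power figures do.

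**The case against.** The strongest reply is that two sentences keep withdrawn patients in the analysis and only one destroys their data, so the authors evidently meant to retain them. That is probably right about intent. A reader might infer that the plan prescribes a complete-case analysis in which recorded endpoints are discarded. The documents do not support that inference: the text is contradictory, and the loss follows only if the destruction sentence prevails. What stands is that staff cannot comply with both, and that acting on the destruction sentence defeats the evident aim.

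A second tempting reading is that any single missing item, even one urine output, removes a patient. The rule is unqualified, so this is a permissible reading, but the plan does not say it.

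Third, destroying a study record does not erase the hospital chart, and Study Procedures holds MRNs for chart access and data verification. This softens the consequence. It does not remove it, since no re-extraction is planned and the destruction sentence makes no exception for the MRN.

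Fourth, a loss that is equal in both arms overlooks the chart pool and the prospective top-up for controls. That stands, and it is why both scenarios are shown: with controls held at 60, the widening of the interval is about half as large.

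Finally, no missingness rate or mechanism is given. The figures show what the rule could cost, not what it will cost. Differential selection of controls is likewise a risk and not a demonstrated bias.

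**Conclusion.** The point holds as a contradiction that must be resolved before data are handled under these rules. The missing-data rule, the undefined intention-to-treat value, the promised analysis of withdrawn patients and the destruction of their information cannot all be followed. If destruction is carried out, the promised intention-to-treat analysis cannot be delivered, and recorded length of stay and weight change leave the study dataset because another item is missing.

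The size is unknown. Within the assumed 10 to 30% range, the length-of-stay interval widens by between 2.8% (intervention arm only, 10%) and 20.1% (both arms, 30%), and a design with exactly 80% power falls to between 77.8% and 64.6%. These figures rest on assumed loss rates and a back-solved effect size. They do not establish that the trial is underpowered or biased.

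**What to change.** - Delete the rule that missing data prompts withdrawal, together with its undefined intention-to-treat value.
- Delete the sentence that destroys information at withdrawal. State instead that data collected up to withdrawal are retained, subject to the consent terms, which were not available for this review.
- Analyse each primary endpoint, with the planned comparison of means, on all enrolled patients in their assigned arm who have that endpoint observed. Do not drop or replace a chart control because another item is missing.
- Report the number missing for each endpoint by arm.
- Optionally, add a sensitivity analysis for missing BNP or weight.

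The cost is protocol wording, possibly consent wording, and a little analysis work, with no extra patients, visits or tests. The change keeps endpoints that were recorded. It does not recover a missing discharge BNP, so the BNP comparison has the same number of patients either way.

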Compression Wraps as adjuvant therapy in the management of acute systolic heart failure (CATAS-HF trial)

8/1/2020

- Study Protocol &
Statistical Analysis Plan

NCT# NCT04095416

STUDY TITLE: Compression wraps as adjuvant therapy in the management of acute systolic heart failure (CATAS-HF)**• STUDY AIM, BACKGROUND, AND DESIGN ABSTRACT**

Our goal is to measure the application of lower extremity compression wrapping as adjuvant therapy to diuresis in the management of patients hospitalized for acute systolic heart failure. Use of compression wrapping will be assessed through randomized parallel intervention clinical trial of patients admitted to Henry Ford Hospital I5 Cardiology service for management of acute systolic heart failure presenting with lower extremity edema. Enrolled patients will be managed with standard medical therapy, with (intervention) or without (control) the adjuvant use of lower extremity compression wrapping. Efficacy of the intervention will be analyzed for the following primary endpoints: 1) Percentage difference in weight before and after diuresis 2) Percent difference in Brain natriuretic peptide (BNP) from admission to discharge; 3) Difference in length of admission in days. Our hypothesis is adjuvant use of lower extremity compression wraps to standard medical therapy increases percentage of weight reduction achieved with diuresis, increases percent reduction in BNP after diuresis, and decreases total length of stay for patients hospitalized with acute systolic heart failure.

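### Shorter stay is a primary endpoint, but the only post-discharge outcome is 30-day readmission, with no vital status, no reason for readmission and no rule for death

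*Combined protocol and SAP*

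**What the plan says.** The Study Aim, Background, and Design Abstract lists as its third primary endpoint "3) Difference in length of admission in days", and the hypothesis is that wrapping "decreases total length of stay for patients hospitalized with acute systolic heart failure".

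Study Procedures sets the period of participation: "Total time of subject enrollment in the study: duration of hospital stay. No additional visits or follow-up testing is required". The same section plans one look beyond discharge. After the control data it says "Research team will also perform chart review on enrolled patients to evaluate for 30-day readmission rate"; for the intervention arm, "These charts will also undergo review by research team to evaluate for 30-day readmission rate". The other items to be collected are the same in both arms: "admission length of stay, daily weights, daily urine outputs, daily diuretic dose and type(s) used, admission BNP, and discharge BNP".

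Anticipated Benefits includes "decreased 30-day readmission rate".

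The Data and Safety Monitoring Plan says "Each patient will be assessed at the start of enrollment, and at the end of hospitalization for compliance with standard medical care". It also requires adverse events and harm events to go to the IRB at once. It sets no time limit on that duty and describes no way of looking for events after discharge.

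Death and vital status are not an outcome or a data item anywhere in the text. Mortality is mentioned only under Alternatives, in a remark about what is not being withheld from controls.

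**The concern.** A trial that treats earlier discharge as success needs a check that patients did not leave too soon. After discharge, the only check here is readmission, and death competes with it: a patient who dies at home on day 10 cannot be readmitted on day 20. If readmissions are simply divided by patients, that death is indistinguishable from an uneventful month. More deaths can lower the readmission rate but cannot raise it, and the plan reads a lower rate as a gain.

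Reason for readmission matters for a related reason. A return for a complication and a planned elective admission count the same, so the rate says little about whether discharge was premature or the wraps did harm.

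The choice is also hard to reverse. Study Procedures has the study data, including the record numbers used to reach the charts, discarded when the study ends. Vital status not recorded by then may be hard to link to patients afterwards.

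**Working it through.** **1. The passages side by side**

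| Question | What the plan provides |
|---|---|
| Is shorter stay an aim? | Yes: hypothesis and third primary endpoint (Design Abstract) |
| When does participation end? | At discharge (Study Procedures) |
| What is looked at later? | 30-day readmission by chart review, both arms (Study Procedures) |
| How is a lower rate read? | As a benefit (Anticipated Benefits) |
| Is vital status or reason for readmission collected? | Neither is listed |
| How does a death enter the rate? | No rule |
| Are adverse events reportable? | Yes, with no time limit (Data and Safety Monitoring Plan) |
| How are they found after discharge? | Not described |

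The plan has no figure of its own to reproduce here. Its 60 per arm is for the continuous primary endpoints, and this point does not depend on it.

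**2. Weight of one death**

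With 60 per arm, one patient is 1/60 = 1.7 percentage points and three are 3/60 = 5 points of the arm's death-or-readmission rate.

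**3. Illustration of the direction**

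All rates are assumptions. Let *d* be the 30-day risk of dying before any readmission, and *r* the readmission risk among patients who do not die first.

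- Readmission rate = (1 − *d*) × *r*
- Death or readmission = (1 − *d*) × *r* + *d*

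With *r* = 20%, *d* = 3% (control) and 10% (wraps):

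- Readmission: 0.97 × 0.20 = 19.4% against 0.90 × 0.20 = 18.0%. Wraps look 1.4 points better.
- Death or readmission: 19.4 + 3 = 22.4% against 18.0 + 10 = 28.0%. Wraps are 5.6 points worse.

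**4. Range**

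With *r* from 15% to 30%:

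| Death, control vs wraps | Readmission alone favours wraps by | Death or readmission worse with wraps by |
|---|---|---|
| 3% vs 3% | 0 | 0 |
| 3% vs 6% | 0.45 to 0.9 points | 2.1 to 2.55 points |
| 5% vs 10% | 0.75 to 1.5 points | 3.5 to 4.25 points |
| 3% vs 10% | 1.05 to 2.1 points | 4.9 to 5.95 points |

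The two measures point in opposite directions whenever deaths are higher with wraps. With equal deaths there is no between-arm bias.

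**5. Extreme case**

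Suppose 20% would be readmitted in each arm and every death replaces one of those readmissions, with death again 3% against 10%. Readmission is then 20 − 3 = 17% against 20 − 10 = 10%, an apparent 7-point benefit, while death or readmission is 20% in both arms. Here even the composite shows no difference, which is why death must also be shown separately.

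**6. What 60 per arm can detect** (normal approximation, two-sided 0.05)

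- Death 3% vs 6%: power 12%.
- Death 3% vs 10%: power 34%.
- Death or readmission 22.4% vs 28.0%: standard error √[(0.224 × 0.776 + 0.280 × 0.720)/60] = 0.0791; 0.056/0.0791 = 0.708. Power is Φ(0.708 − 1.96) + Φ(−0.708 − 1.96) = 0.105 + 0.004, about 11%.

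The added data would serve description and safety, not a test.

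**The case against.** Most of what can be said on the other side limits the point without removing it.

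- *The plan scores deaths as non-readmissions.* A reader might infer this, but no section says so. It is the default arithmetic of a crude rate whose denominator is not defined. The missing-data rule in Study Procedures might be applied to a death instead, leading to withdrawal. A patient who dies after discharge can, however, have every listed in-hospital item complete, so that rule does not clearly apply. If it did, Withdrawal of Subjects says the information is both analysed and destroyed. No reading brings the death into view.
- *Discharged patients fall outside adverse event reporting.* This is also tempting and also unsupported: the reporting duty has no time limit. The end-of-stay assessment is for compliance with standard care, so it does not define a safety window either. What stands is that no post-discharge ascertainment is described.
- *Readmission is the only check on premature discharge.* That goes too far. Percent weight loss and BNP change to discharge are co-primary, and a patient sent home under-decongested would tend to do worse on both. They stop at discharge, though, and cannot show what happens afterwards.
- *Follow-up is absent after discharge.* It is not: the 30-day chart review is passive follow-up, compatible with having no further visits.
- *The effect is speculative and secondary.* This stands in part. Every rate above is assumed, nothing in the documents suggests that deaths will differ by arm, the main scenarios move readmission by about 2 points at most, and readmission is not a primary endpoint. It is nevertheless a claimed benefit and the sole post-discharge outcome.

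**Conclusion.** The point holds as a gap in outcome definition and data collection. The plan rewards shorter stay, follows patients after discharge for readmission alone, and has neither the data nor a rule to distinguish a patient who died from one who stayed well at home. An excess of deaths in one arm would at best go unseen and at worst appear as fewer readmissions.

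The documents do not show that such an excess is likely, and they give no rates from which to size it. Under the assumed rates, the shift in readmission alone is 0.45 to 2.1 points when deaths differ and nil when they do not; the 7-point shift needs every death to replace a readmission. These scenarios also assume that deaths precede any readmission. The case for changing the plan rests on low cost and on the direction of the possible error, not on a demonstrated effect. It is a change that should be made, but the primary comparisons do not depend on it.

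**What to change.** 1. In Study Procedures, extend the planned 30-day chart review in both arms to record vital status at day 30 after discharge, date of death, and the date and main reason for each readmission.
2. Report death or readmission within 30 days of discharge, with death and readmission also shown separately, beside length of stay. Label it a descriptive safety outcome, not a powered test.
3. In Study Procedures and in the Data and Safety Monitoring Plan, state that adverse events found in this review for prospectively enrolled patients are reported to the IRB under the existing rule.

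The cost is a few extra fields in a review the team already performs, with no added visit. Deaths and readmissions outside the health system may be missed. The shortfall may differ between arms, because controls come largely from past admissions (after January 2018) while the wrap arm is prospective. That should be stated as a limitation.
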